4.6. Measures to Minimize Bias

4.6.1. Randomization

At screening, subjects will be assigned a subject screening number in ascending order (per site level), which should not be skipped. When subjects are confirmed to be eligible for the clinical study, they will be assigned a subject randomization number in ascending order. Allocation of each subject to a given treatment will be done using a centralized electronic system (interactive web response system [IWRS]), according to a pre-specified randomization scheme prepared by an independent statistician at the CRO. Subjects will be randomized in a 2:1 ratio to MOR106 or placebo.

4.6.2. Blinding and Unblinding

This is a randomized, double-blind clinical study. The subject and the entire clinical study team, including the investigator, clinical study coordinator, and sponsor personnel are blinded to treatment assignment. Details on unblinding procedures for the interim and primary analysis are in Section 7.3.2).

The site pharmacist(s) or appropriately qualified member of the clinical study staff, are unblinded to treatment and assigned by the investigator to prepare and administer the IMP that corresponds to the assigned subject identification number. All staff members not involved in IMP preparation and/or administration are blinded to treatment assignment. Galapagos MOR106-CL-204

The blind can be broken via IWRS only if the investigator deems it necessary for the safety of a subject. The investigator is encouraged to discuss considerations to break the blind with the CRO medical monitor, whenever possible, and where the situation allows. However, the responsibility to break the treatment code in emergency situations resides solely with the investigator. The investigator is not required to discuss unblinding beforehand if he or she feels rapid emergency unblinding is necessary, but is required to inform the sponsor in a timely fashion after unblinding has occurred.

If the blind is broken for any reason during the course of the clinical study, the moment on which the blind was broken and all other relevant information will be documented by the investigational site. The reason for breaking the blind will be indicated and justified in the source documentation, together with the confirmation that the subject discontinued the study treatment with unblinding as the reason for discontinuation.

If an AE leads to unblinding, the AE will be given as the reason for unblinding. All subjects who are unblinded should, where possible, complete the ETD visit. Any AEs should be followed until resolution.

Code-break information (via IWRS vendor) will be provided to the bioanalytical laboratory responsible for serum drug determination sample analysis, the laboratory responsible for biomarker analysis, and to the sponsor pharmacovigilance lead for SAE reporting purposes.

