9.1. SUBJECT DISPOSITION

Table 14.1.1.1: Subject disposition: Analysis populations

Tabulation per treatment group (and over all subjects) of the number of subjects in each of the analysis populations (screened, randomized, safety/immunogenicity, FAS and PK) defined for the study.

Population: all screened subjects.

Table 14.1.1.2: Subject disposition: Tabulation by country and site

Tabulation per treatment group (and overall) of the number of subjects in each of the countries and sites.

Population: all randomized subjects.

Table 14.1.1.3: Subject disposition: Tabulation of the number of subjects at each time interval

Tabulation per treatment group (and over all subjects) of the number of subjects in each visit/time interval.

Population: safety analysis set.

Table 14.1.1.4: Subject disposition: Study and treatment completion and discontinuation

Table per treatment group (and overall) of completion/discontinuation from study and from study medication and the reason for discontinuation.

Population: safety analysis set.

Table 14.1.1.5: Subject disposition: First and last dates in the study

Summary showing these key dates (regardless of treatment assignment):

- Date of the earliest ICF signed for this study;
- Date of first and of last screening visit (visits as reported in the database);
- Date of first study drug administration;
- Date of last physical visit performed in this study;
- Last date of contact with any subject in this study.

Population: all screened subjects.

Listing 16.2.1.1: Subject disposition: Randomization

Listing per subject showing subject number, ICF date, randomization number, randomization groups, randomization date and time and any information on code breaking:

- the reason for blind broken
- the number of days since first study dose of study medication at the time the subject is unblinded
- the AE preferred term (in case the unblind was due to an AE)
- (verbatim) explanation on the unblinding reason.

Discrepancies between planned and actual randomization groups will be flagged.

Population: all randomized subjects.

Listing 16.2.1.2: Subject disposition: Listing by country and site

Listing per treatment arm showing the country name, the site number and the list of subjects screened at this site.

Population: all randomized subjects.

Listing 16.2.1.3: Subject disposition: Number of days in study

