Listing per treatment group, per subject and per time point showing subject number, the analysis populations inclusions, the actual study day of each visit and the whole study duration.

The whole study duration is derived as last date of contact – date of ICF + 1 day.

Population: safety analysis set.

Listing 16.2.1.4: Subject disposition: Study and treatment completion and discontinuation

Listing per treatment group and per subject showing the study completion or discontinuation status, the number of days since first study treatment administration at study termination and the subject's date of last contact in study. In case of discontinuation, the related reason and any available specifications will also be printed (i.e. the AE reported terms if the discontinuation was due to an AE, etc.).

The treatment completion or discontinuation status will be listed in a similar way.

Population: safety analysis set.

Listing 16.2.1.5: Subject disposition: Study analysis periods

Listing per treatment group and per subject showing the analysis periods, including the start and end dates of each analysis period and the date of first and last study drug administration.

Population: safety analysis set.

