14.1.8. Tables

Analysis periods will be replaced by their respective treatment via the randomization list (i.e., an as-randomized allocation) in all tables and listings.

Table 14.3.1.1: Treatment-emergent adverse events: Summary table

Tabulation per treatment group of the incidence of subjects:

- With at least one treatment-emergent adverse event (TEAE);
- With at least one serious TEAE;
- With at least one ISR;
- With at least one skin related TEAE;
- With at least one ISR (Grade 3 or higher) or skin related TEAE;
- With at least one AE leading to death;
- With at least one mild TEAE as worst intensity per treatment;
- With at least one moderate TEAE as worst intensity per treatment;
- With at least one severe TEAE as worst intensity per treatment;
- With at least one life threatening TEAE as worst intensity per treatment;
- With at least one fatal TEAE as worst intensity per treatment;
- With at least one TEAE considered related to study drug;
- With at least one TEAE for which the study drug was temporarily stopped;
- With at least one TEAE for which the study drug was permanently stopped.

Population: safety analysis set.

Table 14.3.1.2: Treatment-emergent adverse events up to 30 days after last dose: Summary table

Same as [Table 14.3.1.1](#), but restricted to events that started after start of study medication and up to 30 days after last dose.

Population: safety analysis set.

Table 14.3.1.3: Treatment-emergent adverse events: Tabulation of all adverse events

Incidence of subjects tabulation per treatment group of TEAE classified per system organ class and preferred term.

Population: safety analysis set.

Table 14.3.1.4: Treatment-emergent adverse events up to 30 days after last dose: Tabulation of all adverse events

Same as [Table 14.3.1.3](#), but restricted to events that started after start of study medication and up to 30 days after last dose.

Population: safety analysis set.

Table 14.3.1.5: Treatment-emergent adverse events: Tabulation of all adverse events by preferred term

Incidence of subjects tabulation per treatment group of TEAE classified per preferred term.

Population: safety analysis set.

Table 14.3.1.6: Treatment-emergent adverse events up to 30 days after last dose: Tabulation of all adverse events by preferred term

Same as [Table 14.3.1.5](#), but restricted to events that started after start of study medication and up to 30 days after last dose.

Population: safety analysis set.

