Table 14.3.1.7: Treatment-emergent adverse events: Tabulation of all adverse events – Alphabetic order

Same as [Table 14.3.1.3](#) but sorted by alphabetic order.

Population: safety analysis set.

Table 14.3.1.8: Treatment-emergent adverse events up to 30 days after last dose: Tabulation of all adverse events – Alphabetic order

Same as [Table 14.3.1.3](#), but restricted to events that started after start of study medication and up to 30 days after last dose and sorted by alphabetic order.

Population: safety analysis set.

Table 14.3.1.9: Treatment-emergent adverse events: Tabulation per worst intensity

Cross-tabulation of incidence of subjects per treatment group of TEAE preferred terms classified per system organ class versus their intensity. Considering the worst-case intensity per TEAE preferred term and per subject in each treatment group.

Population: safety analysis set.

Table 14.3.1.10: Treatment-emergent adverse events: Tabulation of all treatment-related events

Same as [Table 14.3.1.3](#), but restricted to the AEs categorized as related to study drug.

Population: safety analysis set.

Table 14.3.1.11: Treatment-emergent adverse events: Tabulation of treatment-related events per worst intensity

Same as [Table 14.3.1.9](#), but restricted to the AEs categorized as related to study drug.

Population: safety analysis set.

Table 14.3.1.12: Treatment-emergent adverse events: Tabulation of all injection site reaction events

Same as [Table 14.3.1.3](#), but restricted to the ISR events.

Population: safety analysis set.

Table 14.3.1.13: Treatment-emergent adverse events: Tabulation of all injection site reaction events per worst intensity

Same as [Table 14.3.1.9](#), but restricted to the ISR events.

Population: safety analysis set.

Table 14.3.1.14: Treatment-emergent adverse events: Tabulation of all skin related events

Same as [Table 14.3.1.3](#), but restricted to the skin related events.

Population: safety analysis set.

Table 14.3.1.15: Treatment-emergent adverse events: Tabulation of all skin related events per worst intensity

Same as [Table 14.3.1.9](#), but restricted to the skin related events.

Population: safety analysis set.

Table 14.3.1.16: Treatment-emergent adverse events: Tabulation of all events for which the study or study treatment were discontinued

Same as [Table 14.3.1.3](#), but restricted to the TEAEs for which the study treatment was permanently discontinued, or for which the study was discontinued.

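### After a code break, protocol 4.6.2 has unblinding recorded as the reason for stopping treatment even when an adverse event led to both, so the disposition table can understate adverse events as a reason and disagree with the adverse event tables

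*Protocol*

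**What the plan says.** Protocol 4.6.2 sets the condition for emergency unblinding: "The blind can be broken via IWRS only if the investigator deems it necessary for the safety of a subject". If the blind is broken for any reason, the source documents must justify the break, "together with the confirmation that the subject discontinued the study treatment with unblinding as the reason for discontinuation". The next paragraph places an AE in a separate item: "If an AE leads to unblinding, the AE will be given as the reason for unblinding".

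The SAP uses these reasons in two sets of outputs.

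- **Disposition (SAP 9.1).** Table 14.1.1.4 shows, per arm, "completion/discontinuation from study and from study medication and the reason for discontinuation". Listing 16.2.1.4 adds available specifications of the reason, for instance "the AE reported terms if the discontinuation was due to an AE". Listing 16.2.1.1 covers code breaks and includes "the AE preferred term (in case the unblind was due to an AE").
- **Adverse events (SAP 14.1.8 and 14.1.10).** Table 14.3.1.1 has the row "With at least one TEAE for which the study drug was permanently stopped". Table 14.3.1.16 is "restricted to the TEAEs for which the study treatment was permanently discontinued, or for which the study was discontinued". Listing 16.2.10.12 selects AEs by the action taken with study drug.

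Protocol 4.5.4 separately lists AE-based conditions for stopping IMP, and these do not depend on a code break.

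**The concern.** When an AE leads both to the code break and to the end of treatment, the stop has two candidate reasons. Section 4.6.2 names unblinding, makes no exception for an AE that would itself have ended treatment, and sends the AE to another item. A site that follows it literally files a tolerability stop under an administrative label.

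Reasons for discontinuation are a planned descriptive result in a study whose primary objective is safety and tolerability. The arms are small, so one subject visibly moves a percentage. A reader of the study report could also find different numbers of AE discontinuations in the disposition and safety sections, with no planned explanation.

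**Working it through.** **The plan's own figure.** Protocol 7.1 gives an 87% chance of seeing at least one event among 40 subjects at 5% incidence. 1 − 0.95^40 = 0.8715, so it reproduces. The present point does not depend on it.

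**Tracing one subject.** Take a subject on IMP who has an AE, is unblinded because of it, and receives no further doses.

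| Output | Source of the information | Where the subject appears |
|---|---|---|
| Table 14.1.1.4 | Recorded reason for stopping | Unblinding, if the CRF follows 4.6.2 |
| Listing 16.2.1.4 | Same reason, plus specifications | Unblinding; the AE term is not assured |
| Listing 16.2.1.1 | Reason for unblinding | The AE preferred term is shown |
| Table 14.3.1.1 (last row), Listing 16.2.10.12 | AE record | Counted or listed, if the action taken is permanent discontinuation |
| Table 14.3.1.16 | AE record | Counted, if treatment or study was discontinued for the AE |

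The disposition and AE outputs can therefore disagree for the same person. No rule in the SAP links them.

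**Size per subject.** Inputs are the planned arms of 40 and 20 (protocol 7.1), taking all subjects as dosed.

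| Reclassified subjects in the arm (assumption) | MOR106, k/40 | Placebo, k/20 |
|---|---|---|
| 1 | 2.5 points | 5 points |
| 2 | 5 points | 10 points |
| 3 | 7.5 points | 15 points |

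**How likely is at least one?** The documents give no code-break rate. Assume that 1% or 2% of MOR106 subjects have an AE-driven break at some time.

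- If every such break fell during dosing: 1 − 0.99^40 = 33% and 1 − 0.98^40 = 55%.
- A break after the last dose (Day 43) cannot cause a treatment stop, and follow-up runs to Day 169. If breaks were spread evenly (a second assumption), the share during dosing is (43 − 1)/(169 − 1) = 42/168 = 25%. The rates become 0.25% and 0.5%: 1 − 0.9975^40 = 9.5% and 1 − 0.995^40 = 18.2%.

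Under these assumptions the chance of at least one affected MOR106 subject is 9.5% to 33% at a 1% rate, or 18% to 55% at 2%. These figures illustrate the scale; they are not estimates from the plan.

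**The case against.** The strongest reply is that nothing important is lost. A reader might infer that 4.6.2 removes AE discontinuations from the results in the subjects with the worst events. The documents do not support that. SAP 8.1.7.2 takes TEAEs leading to premature discontinuation of IMP from AE records, which 4.6.2 does not govern. The AE stays in the TEAE tables, and Listing 16.2.1.1 shows it beside the code break. The primary endpoint is the incidence and severity of TEAEs, SAEs and AESIs, so it is untouched. This part of the reply stands.

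A reader might also infer that the disposition counts will certainly be wrong. That is not shown either. Section 4.6.2 describes source documentation, and the coding of the CRF disposition field is not in the documents. A safety-motivated break need not come from an AE, since 4.6.2 treats an AE as one possible cause. Nothing says that a subject already stopped for an AE must be relabelled after a later break. Listing 16.2.1.4 is worded openly enough that it might still print the AE term.

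Finally, one can argue that 4.6.2 already captures both facts: the immediate reason (unblinding) and the underlying one (the AE). That is true in the source documents. It does not help Table 14.1.1.4, which tabulates the discontinuation reason without the reason for unblinding.

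**Conclusion.** The point holds as a recording inconsistency with a limited effect. Following 4.6.2 literally can understate AE as a reason for treatment discontinuation in Table 14.1.1.4, by 2.5 points per MOR106 subject or 5 points per placebo subject, and can leave that table at odds with Table 14.3.1.16. This requires three things: an AE-driven code break, a resulting stop before dosing is complete, and a CRF field that follows the protocol wording. The number of such subjects is unknown and probably small. The conclusion reaches only the reason category in the disposition outputs and their agreement with the AE tables. It is a minor point, worth correcting because the correction is so cheap.

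**What to change.** **Protocol 4.6.2.** Replace the required wording with a rule such as: where treatment is discontinued, the event that led to the stop (for example the AE) is recorded as the reason for discontinuation; unblinding and its date are recorded separately.

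**SAP, Table 14.1.1.4.** For subjects who stopped IMP early with unblinding as the recorded reason and an AE as the reason for unblinding, show them under AE or identify them in a footnote. Do not apply this to subjects unblinded after completing dosing; a rule based only on the reason for unblinding would turn treatment completers into AE discontinuations.

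**Reconciliation.** Compare these subjects one by one with Table 14.3.1.16 and explain any difference. Matching totals is not the right test, because Table 14.3.1.16 also includes AEs that led to study discontinuation. The last row of Table 14.3.1.1 is the closer comparison.

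The cost is one protocol sentence, one derivation or footnote, and a short subject-level check. The AE behind a code break is already planned for Listing 16.2.1.1, so no new data are needed for the SAP part, which is sufficient alone if the protocol can no longer be amended. The change concerns only how the reason is recorded, not whether treatment stops.

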4.6.3. Independent Safety Review Committee

To safeguard the safety of the subjects, an independent Safety Review Committee consisting of independent dermatology and statistical experts will be implemented to review accumulating unblinded safety data for the clinical study, specifically the review of any skin related AEs and serious adverse reactions. The specific responsibilities, composition, meeting formats and details of output provided for the meetings of the independent Safety Review Committee will be outlined in detail in an Independent Safety Committee Charter. Members of the independent Safety Review Committee will not be involved in the day-to-day conduct of the study.

5. INVESTIGATIONAL MEDICINAL PRODUCTS

5.1. Identity of the Investigational Medicinal Products

MOR106

The active pharmaceutical ingredient (API) of MOR106 is a human IgG1 monoclonal antibody that binds with a high apparent affinity to human IL-17C.

For s.c. injection the API of MOR106 is formulated as a sterile, stable and highly concentrated liquid formulation of 160 mg/mL filled in a 2R clear glass vial with a rubber stopper and blue crimp cap with an extractable volume of 1 mL. The formulation buffer for s.c. injection consists of L-histidine, L-Arginine, and 0.02% Polysorbate 20, pH 6.0.

Placebo

For s.c injections of placebo sterile formulation buffer of MOR106 in 2R clear glass vial with a rubber stopper and blue crimp cap with an extractable volume of 1 mL is available.

5.2. Dosage and Administration

The IMP will be prepared by an unblinded and adequately trained member of the clinical center pharmacy staff as designated by the principal investigator.

S.c. injections of MOR106 or placebo will be performed by an unblinded administrator who is not performing or involved in any of the study assessments.

Appropriate measures will be taken to keep the subjects blinded from the administered IMP. Details will be provided in the study reference manual.

For the single dose s.c. injection, the following components will be supplied to the clinical centers:

- Vials containing 160 mg/mL MOR106 injectable solution, buffered at a pH 6.0.
- Vials containing formulation buffer of MOR106, pH 6.0 (Placebo).

The following doses will be used:

- MOR106 320 mg (2 mL at 160 mg/mL) every 2 weeks (Q2W) s.c. injection, including a LD of 2 x 320 mg in total (2 x 2 mL) on Day 1.
- Corresponding placebo s.c. injection (2 mL formulation buffer) plus an additional s.c. injection (2 mL) on Day 1.

S.c. injection sites should be alternated among the different quadrants of the abdomen (avoiding the navel and waist areas) so that the same site is not injected for two consecutive visits. The quadrant injected should be documented in the CRF. Full details on the s.c. administration will be provided in the pharmacy manual. To allow for adequate assessment of the ISRs study treatment should be administered into an area of normal looking skin (where possible). Instructions for assessing and recording ISRs will be provided in the study reference manual.

The dose-corresponding-volume of MOR106 drug product for s.c. injection will be collected in a syringe and injected with a suitable hypodermic needle for s.c. injection. As placebo, the same volume of placebo solution as the dose-corresponding-volume of MOR106 drug product, will be collected in a syringe and injected with a suitable hypodermic needle for s.c. injection.

Detailed instructions on IMP management will be provided in the pharmacy manual.

5.3. Packaging, Labeling and Distribution

IMP packages will be labeled with clinical study-specific details, including storage conditions.

All manufacturing, packaging, and labeling operations will be performed according to Good Manufacturing Practice for Medicinal Products and the relevant regulatory requirements.

The distribution of the IMP to the clinical site will only occur after the required local documentation is obtained including clinical study approval by Competent Authorities and

5.4. Storage

Sites are to store the IMP supplies in a secure area at 2-8°C (i.e. 36-46 °F) until dispensed. Sites will be required to monitor the storage temperature by using a suitable temperaturerecording device in order to establish a record of compliance with these storage conditions.

Details for the appropriate monitoring of the storage temperature and handling of temperature excursions will be provided in the pharmacy manual.

5.5. Treatment Compliance and Drug Accountability

The pharmacist or other designated clinical site personnel should maintain a log of the total amount of IMP received at site, date/time of IMP preparation, and administration to the subjects. IMP supplies for each subject will be inventoried and accounted for throughout the clinical study. At the end of the treatment period these records will be checked against the inventory by the study monitor. All IMP supplies will be stored in locked facilities.

Upon sponsor approval all unused IMP and empty IMP packages will be destroyed at the site. If destruction by the site is not possible or the destruction process is found unacceptable by the sponsor, the IMP should be returned to the drug supplier/drug depot as appropriate.

Detailed instructions on IMP handling will be provided in the pharmacy manual.

